13.0 CONCOMITANT THERAPY/INTERVENTION

13.1 General

Prior to enrolling in CTN-0107, participants may have pre-existing relationships with professionals and paraprofessionals involved with SUD treatment, including a medical provider, CPSS, 12-step sponsor, and/or a social worker. Renewed or continued contact with any such professional or paraprofessional staff may include MOUD or other substance use disorder treatment. Regardless of study group, impeding any such contacts would be both unethical and infeasible. To account for non-study related professional or paraprofessional contacts, participants will be asked about such exposures during follow-up assessments.

14.0 STATISTICAL DESIGN AND ANALYSES

14.1 General Design

This study is a 2-arm, pragmatic, randomized, prospective pilot trial evaluating the effectiveness of PILOT compared with TAU on the frequency of self-reported overdose risk behaviors at 180 days after Index ED admission.

14.1.1 Study Hypothesis and Objectives

The primary hypothesis of this trial is that PILOT will result in a reduction in self-reported overdose risk behaviors at 180 days after Index ED admission as compared with TAU.

Key secondary hypotheses are that PILOT will result in a reduction of self-reported overdose risk behaviors at 30 days and 90 days, with the same hypothesis above, but at the different month time points.

The secondary objective of the trial includes the following:

1. Assess number of steps achieved along a modified SUD Cascade of Care for those randomized to PILOT vs. TAU.
2. Assess whether NFOO survivors within an ED setting are willing to engage in study procedures and with peer support services using the PILOT model and length of engagement and enrollment in PILOT among those randomized to pilot.

Exploratory objectives include the following. In situations of comparison between TAU and PILOT, the null hypothesis is that there is no difference between the two, and the alternative is that there is a difference.

1. Assess the effects of PILOT versus TAU on achievement of each individual step in the modified OUD Cascade of Care at 180 days, as well as 30 days and 90 days.
2. Evaluate the effectiveness of PILOT versus TAU of initiation on medications for OUD in the ED, among those participants with OUD.
3. Assess the effects of PILOT versus TAU on substance use frequency at 30-, 90-, and 180-days.
4. Evaluate the degree of engagement in Peer Support Services for participants randomized to PILOT at 30-, 90-, and 180-days, measured as number of contacts received or initiated with a Peer Support Specialist in the past month.
5. Evaluate the effectiveness of PILOT versus TAU on self-reported attendance in 12-step meetings, peer support services, other recognized recovery organization, or formal SUD treatment at any time during study participation.
6. Evaluate the effectiveness of PILOT versus TAU on percent of toxicology screens positive for opioids other than buprenorphine or methadone.

7. Evaluate the effectiveness of PILOT versus TAU on repeat non-fatal overdose and 210-day rates of death.

The primary outcome measure for the primary objective and key secondary hypotheses is the frequency of self-reported overdose risk behaviors at 180 days after Index ED admission as defined in **Section 7.1**, measured as a total score from 11 items ranging from 0 to 44.

The outcome measures for the secondary objectives are:

1. Number of steps achieved on the modified SUD Cascade of Care
2. Number accepting the intervention (to possibly engage with CPPSs using the PILOT model) compared with number approached
3. Length of time from baseline to last meeting with the PILOT intervention/counselor

Participants will be recruited at each ED site. Research staff assigned to the study will work during times to include evenings and weekends to ensure success with enrollment. Research staff will identify patients seen in the ED by screening, reviewing the ED trackboards, and by provider or peer referral. A member of the research team will keep a log of all patients screened and excluded and the reasons for exclusion. Potential participants identified will be evaluated by research staff for eligibility.

14.1.2 Randomization and Factors for Stratification

Eligible participants will be randomized in a 1:1 ratio to PILOT or TAU after confirmation of study eligibility status and baseline assessments have been completed. The randomization process will be performed by computer by the DSC. A permuted block randomization procedure with random block sizes will be implemented to balance per site and homelessness status (yes/no).

The randomization procedure will be conducted centrally through the DSC, and randomization details such as block size will not be conveyed to staff or participants. The DSC statistician will generate the randomization schedule using balanced blocks of varying sizes within strata to ensure lack of predictability along with relative equality of assignment across treatment groups. The DSC statistician will review randomization data on a regular basis to ensure that the scheme is being implemented according to plan. If a participant drops out of the study at any point after randomization, the randomization slot will not be re-allocated to a new patient due to the intent-to-treat nature of the study.

14.2 Rationale for Sample Size and Statistical Power

Power analyses and sample size calculation was performed with respect to the first specific aim of the primary objective: comparing PILOT to TAU on the basis of the frequency of self-reported overdose risk behaviors at 180 days. This was conducted via simulation. The simulations required specifying the data generating/simulation process and a hypothesis test.

The self-reported overdose risk behaviors to be used for this trial are modified and expanded from one used by Bohnert, et al (2016) [23]. In their version, the maximum score was 32 and they found an average of 3.3 and 3.8 in their control and intervention groups, respectively, at baseline.

They used a Poisson regression model to assess their intervention effect. Their estimated intervention effect was a 0.72 rate ratio (RR). To this end, for the power simulations presented here, a mean of 3.55 was considered, with a treatment effect of 0.72. For each (simulated) participant, a baseline score was generated from a Poisson distribution with a mean, or λ value, of 3.55. As a Poisson regression model with covariates for baseline score, treatment, site, and stratum will be used for power simulation purposes, coefficients for each must be specified for the simulation. The coefficients for site and stratum were set to 0 to specify no effect of either. Bohnert, et al (2016) reported a coefficient of approximately 0.068, $\ln(1.07)$, for the baseline score coefficient, which will also be used here. The intercept was set as approximately 1.03, from setting $\ln(\lambda) = \beta_0 + \ln(1.07) \times \text{baseline}$ and solving for β_0 (assuming both λ and *baseline* are 3.55 to match the TAU case). The post-treatment outcome value for those assigned to TAU was generated from a Poisson distribution with a mean of $\exp(1.03 + \ln(1.07) \times \text{baseline})$, where *baseline* was their generated baseline score. For participants assigned to PILOT, their post-treatment outcome value was generated from a Poisson distribution with a mean of $\exp(1.03 + \ln(1.07) \times \text{baseline} + \ln(0.72))$, to achieve the desired 0.72 RR for the same baseline values. Site (3 levels) and stratum (2 levels) were also generated for each participant but, again, had no effect on the outcome.

After data was simulated, a Poisson regression model was fit with fixed effects for baseline score, treatment, site, and strata. Treatment was declared significant if the p-value for the treatment coefficient was strictly less than 0.05. The entire process was repeated 10,000 times. The proportion of times the treatment was significant is an estimate of the power for the scenario.

To assess the sensitivity of the results to the assumptions made, differing values for the specified simulation parameters were also considered. Specifically, values of 2.8, 3.3, 3.8, and 4.3 were considered in place of the 3.55 mean at baseline. Given that this trial will use an expanded version of the risk behaviors used in Bohnert, et al (2016), it would be reasonable to guess that the mean frequency at baseline for this trial would higher. However, a higher value actually (as will be shown) increases power, so the 3.55 mean used here can be viewed as conservative. Larger values of 5, 10, 15, 20, 25 were also used to clearly show this pattern. Also considered were different values of the RR: 0.70, 0.74, 0.76, 0.78, and 0.80. Note that values closer to 1 are weaker effects and would thus have lower power with all other settings fixed.

Results are presented in the table and two figures below. With a mean of 3.55 at baseline and a RR of 3.55, there is over 90% power to detect the difference with a sample size of 150. There is over 80% power with a lower sample size of 100 as well. Power increases as the mean at baseline increases, as shown by Table 2 and the Power Results by Mean at Baseline figure. At a mean at baseline of as low as 2.8, there is still over 85% power to detect a RR of 0.72 with a sample size of 150. Power also increased as the RR decreased. With a sample size of 150 and a mean at baseline of 3.55, there is over 80% power to detect a difference of up to 0.76. The initial estimate of a 0.72 RR by Bohnert, et al (2016) came from data on participants who possibly didn't experience an overdose. Their estimate of RR in just the group experiencing an overdose was 0.65. Their intervention also consisted of just a 30-minute motivation interview session by a therapist, along with control procedures, as compared to peer mentorship that will be used in this trial. So, while the simulation results here are sensitive to changes in treatment effect (RR), there

is reason to believe the value of 0.72 used is conservative. For these reasons (greater than 90% power at specified parameters, relative robustness to their specification), a sample size of 150 is justified for this trial.

14.3 Table 2: Power Results

		Total Sample Size		
Mean Score at Baseline	Rate Ratio	100	125	150
2.8	0.70	75.99%	85.48%	91.00%
	0.72	69.31%	79.20%	86.92%
	0.74	63.02%	73.39%	80.73%
	0.76	54.99%	65.55%	74.58%
	0.78	47.62%	57.87%	66.25%
	0.80	40.90%	49.40%	56.61%
3.3	0.70	82.99%	90.65%	95.14%
	0.72	76.74%	85.59%	91.56%
	0.74	70.58%	80.35%	86.68%
	0.76	62.24%	72.37%	80.79%
	0.78	54.51%	65.21%	73.33%
	0.80	46.46%	56.24%	63.67%
3.55	0.70	85.48%	92.75%	96.15%
	0.72	80.08%	88.34%	93.32%
	0.74	73.70%	82.60%	89.23%
	0.76	65.15%	76.12%	83.57%
	0.78	58.49%	67.16%	76.19%
	0.80	49.38%	59.03%	67.69%
3.8	0.70	88.40%	93.99%	97.42%
	0.72	82.30%	90.18%	94.83%
	0.74	76.37%	85.09%	90.98%
	0.76	68.74%	78.61%	85.65%
	0.78	60.08%	71.62%	78.76%
	0.80	52.01%	61.83%	69.92%

		Total Sample Size		
Mean Score at Baseline	Rate Ratio	100	125	150
4.3	0.70	91.46%	96.19%	98.46%
	0.72	86.85%	93.33%	96.79%
	0.74	81.08%	89.28%	93.58%
	0.76	73.69%	83.15%	89.91%
	0.78	65.87%	75.77%	83.44%
	0.80	57.54%	67.32%	75.98%

Figure 3: Power Results by RR

[figure not shown]
[figure not shown]

Figure 4: Power Results by Mean at Baseline

14.3.1 Projected Number of Sites

The anticipated and projected number of sites is three. This was chosen based on preliminarily-identified sites that had peer-led ED programs already instituted.

14.3.2 Projected Number of Participants per Site

This study will enroll a total of approximately 150 participants, for an expected number of approximately 50 per site.

14.4 Statistical Methods for Primary and Secondary Outcomes

Primary Outcome

The primary outcome of number of self-reported overdose risk behaviors at 180 days after Index ED admission, measured as the total score, will be analyzed with a longitudinal mixed effect Poisson regression model incorporating total score at earlier time points as well as 180 days. Fixed effect covariates for baseline score, treatment, days, site, stratum, and an interaction between treatment and days. Days will enter the model as a categorical covariate, as opposed to continuous, to allow greater flexibility. A random effect is included to account for correlation within each participant. The template SAS code to fit this model is given below.

```
pproc glimmix data = data;
  class site days participant;
  model risks = baseline trt|days site strat / dist = poisson link = log;
  random intercept / subject = participant;
run;
```

where data is the dataset, risks is the outcome, baseline is the participants risk behavior score at baseline, trt is a treatment indicator with a value of 1 indicating PILOT and 0 indicating TAU, days is the day number of the visit, and site and strat are variables corresponding to the participant's site and stratum level respectively.

The treatment effect of PILOT from this model will be given as a rate ratio (RR; as the exponential of the treatment and days interaction at 180 days plus the main effect of treatment) along with 95% confidence interval. This can be interpreted, conditionally, as a ratio of the mean risk behaviors for those assigned to PILOT divided by the mean risk behaviors for those assigned to TAU at 180 days, while all other variables (specifically including the baseline value) are the same. A value of 1 for the RR is the pivotal value. An RR of less than 1 would indicate less opioid risk behaviors for those assigned to PILOT compared to those assigned to TAU. A p-value will also be provided, testing whether there was a significant effect of PILOT versus TAU. If the p-value is strictly less than 0.05, there is a significant effect.

Key secondary hypotheses are this same outcome, but at 30 and 90 days, as opposed to 180 days. These will be analyzed in the same manner.

Secondary Outcomes

A secondary outcome is the number of steps achieved along a modified SUD Cascade of Care. This will be modeled similar to the primary outcome, an over dispersed Poisson regression model with fixed effect covariates for treatment, site, and stratum. Note that no baseline score covariate is included as all participants will be considered to have achieved 0 steps at baseline. Similar to the primary outcome, a RR along with 95% confidence interval and p-value will be given from this model to determine the effect and significance of PILOT as compared to TAU.

An important point to consider is that participants entering the trial may not have a primary diagnosis of OUD, or even SUD. Because of this, some steps are not inherently eligible to them at baseline. However, during the study, the participant may endorse OUD, or some SUD if none were at baseline, and become eligible for these steps. The approach taken here for the prespecified analysis method is that of protection/balanced by randomization. Participants entering without OUD, or no SUD, are likely to be balanced between treatment groups due to random assignment to treatment group (based on baseline DSM-5 SUD diagnoses), such that the effects of this would be equal between PILOT and FORCE. Additional supportive analyses, such as looking at OUD, SUD other than OUD, and no SUD subgroups as determined at baseline, are possible to examine possible chance imbalance between PILOT and FORCE.

For the other secondary outcomes, the number of participants approached and number who were willing to engage with CPPSSs using the PILOT model, as well as percent of those approached who were willing to engage, will be summarized. A 95% confidence interval will be provided for this percent. The length of engagement with PILOT will be similarly summarized.

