2.0 STUDY SYNOPSIS

2.1 Study Objectives

The primary objective of this study is to advance understanding and improve outcomes for individuals who present to an Emergency Department (ED) after surviving a non-fatal overdose involving opioids (NFOO). To achieve this objective, the study will evaluate the preliminary effectiveness of a specialized, enhanced peer recovery intervention tailored for NFOO survivors, called Peer Intervention to Link Overdose Survivors to Treatment (PILOT), on self-reported overdose risk behaviors for individuals who present to the ED after a NFOO. The PILOT intervention will be compared to treatment as usual (TAU) in the ED setting.

The secondary objectives of the study are to: 1) evaluate the number of steps achieved along a modified Substance Use Disorder (SUD) Cascade of Care for individuals randomized to PILOT vs TAU, and 2) to assess whether NFOO survivors within an ED setting are willing to engage with overdose peer support using the PILOT model (feasibility).

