2.2 Study Design and Outcomes

This is a multi-site, prospective, randomized, controlled pilot trial comparing the PILOT intervention with Treatment as Usual (TAU) on the frequency of self-reported overdose risk behaviors for those who survive a NFOO and present to the ED.

The first aim of this study is to test the hypothesis that PILOT will lead to a reduced frequency of self-reported overdose risk behaviors among NFOO survivors at 180 days (end of treatment) compared to TAU (primary outcome measure).

The secondary aims of the study are to: 1) evaluate the number of steps achieved along a modified SUD Cascade of Care among individuals with a recent NFOO, and 2) assess whether NFOO survivors within an ED setting are willing to engage in study procedures and with peer support specialists, measured by (a) the number of potentially eligible patients approached compared with the number willing to be enrolled, and (b) the length of engagement and enrollment in PILOT among those willing to be enrolled and randomized to PILOT.

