### **3.1.5 Approached Population**

The approached population consists of all individuals who were approached in the ED for possible participation in the study, including those who did and did not provide verbal consent for further assessment of eligibility.

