#### **7.4.2 Engagement with the Study and PILOT Intervention**

The assessment of whether recent NFOO survivors within an ED setting are willing to engage with peer support services will be measured by (a) the number of potentially eligible patients approached (Screening Approach form; SCA) compared with the number willing to be enrolled (provided verbal consent; ENRA or ENRY form), and (b) the length of engagement and enrollment in PILOT among those willing to be enrolled and randomized to PILOT. The length of engagement will be calculated from the day of randomization to the last day a PILOT participant was assessed as “Engaged” or “Partially Engaged” on the PIL form.

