### 7.5.2 Engagement with the Study and PILOT Intervention

For engagement with the study and with the PILOT intervention, the number of participants approached (from SCA form) and number who were willing to engage with PILOT peers, as well as the percent of those approached who were willing to engage, will be summarized. A 95% confidence interval will be provided for this percent. The length of engagement with PILOT will be similarly summarized. The template SAS code for these two analyses is given below:

```
proc freq data = secondout_consented;
  tables consented / binomial(level = 'Yes' CL = wald);
  weight count;
run;
```

where:

- *secondout\_consented* is the summarized dataset containing numbers of participants who provided or did not provide written informed consent to participate,
- *consented* is a categorical variable which has "Yes" and "No" responses, with "Yes" being consented to participate in the study (EC0107A.S07CNSNT or EC0107Y.S07CNSNT), and

- *count* is the number of participants who provided the corresponding response, out of patients approached for the study (SCA.SCNPTAPR).

This analysis generates the binomial proportion (with Wald confidence limits) for those consenting to be in the study.

```
proc means data = secondout_length mean std p25 p50 p75 min max clm;  
  var length;  
run;
```

where:

- *secondout\_length* is the dataset containing for each participant in PILOT treatment arm the days since randomization for each peer intervention,
- *length* is the number of days between the randomization date and the last intervention for that participant, as indicated on the PIL form in PILOT treatment arm (PIL.PIENGACT, PI2.P2ENGACT, ..., PI7.P7ENGACT).

This analysis generates descriptive summary statistics (mean, standard deviation, quantiles, and range) for the duration of engagement in the PILOT intervention.

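### The percent reported as willing to engage with PILOT peers counts pre-randomization consent, on two conflicting definitions, and no planned table gives the share of the PILOT arm that ever engaged

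*Protocol*

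**What the plan says.** Protocol 2.1 states the second secondary objective as "to assess whether NFOO survivors within an ED setting are willing to engage with overdose peer support using the PILOT model (feasibility"). Protocol 2.2 is broader: it asks whether survivors "are willing to engage in study procedures and with peer support specialists". Protocol 5.3 and 7.2 then define two measures: (a) patients approached against those willing to be enrolled, and (b) length of engagement among those randomized to PILOT.

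The label of measure (a) shifts in the statistical sections. Protocol 14.1.1 lists it as "Number accepting the intervention (to possibly engage with CPPSs using the PILOT model) compared with number approached". Protocol 14.4 turns it into willingness to engage with the peers, and plans to summarize the "number who were willing to engage with CPPSSs using the PILOT model, as well as percent of those approached who were willing to engage". SAP 7.5.2 keeps that label; its wording is "number who were willing to engage with PILOT peers, as well as the percent of those approached who were willing to engage".

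For measure (b), SAP 7.4.2 ends the length at the last rating of Engaged or Partially Engaged on the Peer Intervention Log ("The length of engagement will be calculated from the day of randomization to the last day a PILOT participant was assessed as" being in either category), and Table 37 repeats this. The code notes in SAP 7.5.2 instead end the length at the last intervention logged in the PIENGACT variables. Protocol 7.2 ends it at the last meeting with the PILOT peer.

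**The concern.** A reader of the final report will take a percent labelled as willingness to engage with PILOT peers as evidence that survivors accept the intervention. Consent is obtained before anyone knows their arm, and under 1:1 allocation about half of those enrolled are never offered a PILOT peer. If part of the PILOT arm never takes up the peer, this percent does not register it, and the length summary may leave those people out or credit them with days.

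Protocol 6.2 ties feasibility to the decision on a larger trial. Uptake among those offered the peer is a basic quantity for planning that trial, and neither secondary measure supplies it.

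**Working it through.** The documents set no target, precision or power for this outcome, so there is no plan figure to reproduce. The check compares definitions and then sizes the effect under stated assumptions.

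**1. Measure (a), side by side**

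| Place | Label | What is counted |
|---|---|---|
| Protocol 5.3, 7.2 | Willing to be enrolled | No form named |
| Protocol 14.1.1, 14.4 | Accepting the intervention; willing to engage with peers | No form named |
| SAP 7.4.2, Table 36 | Willing to be enrolled | Verbal consent, ENRA or ENRY form |
| SAP 7.5.2 | Willing to engage with PILOT peers | Written consent, with Yes meaning "being consented to participate in the study" |

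Under Protocol 10.1, verbal consent covers the screening forms and comes before interest in the study is asked. Under SAP 3.1.1, ENRY holds people who are not interested or not eligible. On the Table 36 definition, a person who agrees to screening and then declines the trial therefore counts as willing. SAP 7.5.2 describes written consent but takes it from a variable on the A and Y forms, the preliminary-screening segments. SAP 3.1.2 places informed consent on Segment C. Which consent that variable records is not stated.

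**2. Does measure (a) respond to uptake?** The sequence in Protocol 10.1 to 10.5 is verbal consent, interest, written consent, randomization, then contact with a PILOT peer for the PILOT arm only. With C consents among A approached, the percent is C/A. Both candidate values of C are fixed before randomization, so C/A is the same whether none or all of the PILOT arm takes up the peer.

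**3. Measure (b) for a participant who never engages**

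- SAP 7.4.2 and Table 37: Unengaged is a planned category (Table 19). A participant always rated Unengaged has no qualifying day and so no length. PROC MEANS omits missing values, and SAP 7.9 plans no missing-data handling for this outcome.
- SAP 7.5.2: the end point is the last logged intervention. SAP 6.2 records attempted contacts in PIENGACT and expects at least weekly attempts. If attempts count, a never-engager receives a positive length.

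**4. Size (illustration only)**

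Inputs: PILOT arm 150/2 = 75 (Protocol 2.3). The never-engaged share u and a mean of 120 days among engagers are assumptions.

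- Never-engagers dropped: reported mean / whole-arm mean = 1/(1-u). This is 1/0.98 = 1.02, 1/0.90 = 1.11, 1/0.80 = 1.25 and 1/0.70 = 1.43.
- At u = 20%: 15 of 75 never engage, so uptake is 60/75 = 80.0% (Wilson 95% CI 69.6 to 87.5%). The whole-arm mean is 120 x 0.80 = 96 days, against 120 reported.
- Attempts counted, u = 20%, and never-engagers credited as an extreme with the full 180 days: 0.80 x 120 + 0.20 x 180 = 132 days, against 96.

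**5. Do other tables fill the gap?** Table 18 gives early terminations with reasons, including refusal, but pools people who never started with people who stopped later. Table 19 counts contacts by engagement category. Table 20 counts peer time by period, with a zero-minutes column. None counts participants who ever engaged.

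**The case against.** The strongest reply is that measure (a) matches its definition. Protocol 2.2 and 14.1.1 include engagement in study procedures, and Protocol 5.3 and 7.2 define (a) as approached against willing to be enrolled. The measure is descriptive, and none of the four milestones in Protocol 7.4 sets a threshold on it. This stands: enrollment willingness belongs in the aim. It does not rescue the label in Protocol 14.4 and SAP 7.5.2, or the verbal-versus-written conflict.

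A second reply is that non-uptake may be rare. Protocol 4.2 reports that 230 of 235 people approached (98%) agreed to FORCE services. If u were near 2%, the inflation would be 1.02. That figure is agreement to an observational service, not uptake in this trial, but it is a fair low end.

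Three stronger readings are tempting and are not supported:

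- A reader might infer that non-uptake will be invisible. Tables 18 to 20 show refusals, contacts with Unengaged participants and zero peer time, and Exploratory Aim 4 summarizes recent peer contacts. Only the participant-level count is missing.
- A reader might infer that community recruits enter the numerator but not the denominator. The SAP's table list assigns Table 36 to the Approached population, defined as "all individuals who were approached in the ED for possible participation in the study". Nothing says the approach form omits community approaches, and community recruitment is only a contingency (Protocol 8.4.1.2).
- A reader might take FORCE's 58% still active at 9 months (133/230) as a guide to non-uptake. It is a retention figure.

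Uptake is also not the same as willingness. Death, incarceration or loss of contact can prevent engagement by someone who was willing.

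**Conclusion.** The point holds in a limited form. Measure (a) is a pre-randomization consent proportion that carries the wrong label in Protocol 14.4 and SAP 7.5.2 and has two incompatible numerators in the SAP. Measure (b) has two incompatible end points in the SAP and no stated value for never-engagers. No planned table reports how many PILOT participants ever engaged.

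That measure (a) cannot reflect uptake follows from the order of events and needs no assumption. The size of the distortion in length is unknown, because the documents give no never-engaged share: 1.02 to 1.43 for u from 2% to 30%, and only if length is built as in SAP 7.4.2 and Table 37. Exclusion of never-engagers is inferred from the absence of a rule; the SAP does not state it, and Table 37 is assigned to the ITT population. Under SAP 7.5.2 the error could instead come from days credited for attempts.

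**What to change.** Amend SAP 7.4.2, 7.5.2 and Tables 36 and 37, and note the change of label from Protocol 14.1.1 and 14.4:

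1. Use one numerator for measure (a): people who agreed to enroll by written consent, excluding decliners recorded on ENRY, over those approached. Name the form and variable. Label it *willing to enroll in the trial*.
2. Add PILOT uptake: the number and percent of all randomized to PILOT with at least one Engaged or Partially Engaged rating, or with at least one completed peer contact, with a 95% CI. Choose one criterion in advance and label the result uptake. A Wilson interval is safer than Wald here, since with 75 of 75 engaged Wald collapses to 100 to 100% while Wilson gives 95.1 to 100%. If completed contacts are used, check the codes first: SAP 6.2 gives 01 for attempted and 01 or 02 for completed, so as written every attempt also counts as completed.
3. Use one length definition that ignores attempted-only contacts, with 0 days for those who never engage, so that N in Table 37 equals all randomized to PILOT.

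The cost is SAP wording and one added row; the Peer Intervention Log already holds the data for items 2 and 3. The downside is that reported willingness and mean length may look less favourable.
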